2.1. Primary objective

The objective is to compare the 5-year overall survival of patients receiving chemotherapy followed by liver transplantation (C + LT) to that of patients receiving chemotherapy alone (C).

2.2. Secondary objectives

- Compare overall survival at 3 years between the two arms.
- Compare progression-free survival at 3 years and 5 years between the two arms.
- Evaluate recurrence-free survival at 3 years and 5 years in arm C + LT.
- Evaluate the recurrence rate at 3 years and 5 years in arm C + LT.
- Compare the quality of life between the two arms.

3. Definition of the study populations

3.1. Description of protocol deviations

The protocol deviations described below will be discussed during a data review meeting with the investigator to define major discrepancies and minor discrepancies:

- Non-compliance with inclusion and/or exclusion criteria.
- Non-adherence to the treatment defined by randomization:
 - For patients randomized to arm C+LT:
 - Time between the last chemotherapy cycle and LT \geq 3 months (major discrepancy).
 - Patient transplanted with progression on the pre-LT CT scan (major discrepancy).
 - Patient not transplanted (major discrepancy).
 - For patient randomized to arm C:
 - Patient who did not receive chemotherapy (major discrepancy).
 - Patient who underwent LT or resection (major discrepancy).
- Variables necessary for primary and secondary outcome criteria not provided:
 - Vital status or information on patient recurrence or progression is missing as of the last update.
 - Patient deceased with an undisclosed date of death.
 - Recurrence or progression occurred, but the date is not specified.
 - Visit date is not provided even though the visit took place.
 - Quality of life questionnaire not completed.

- Deviations from scheduled protocol visits: Visit not conducted as scheduled in the protocol.
- Deviations from protocol-specified timelines:
 - Delay exceeding 6 months between screening and inclusion.
 - No imaging results (MRI, CT scan, PET scan) from within the last 2 months before inclusion.
- Premature study discontinuation.

[figure not shown]
3.2. Descriptions of populations

Several populations will be considered in the analysis:

- **Patients selected by the local committee to be evaluated for inclusion:** This population consists of patients who have signed a consent, whether preliminary or final.
- **Enrolled patients:** This population comprises patients who have signed a final consent and are considered eligible by the validation committee. It includes properly enrolled patients (meeting all inclusion criteria and not meeting any exclusion criteria) and incorrectly enrolled patients (having at least one deviation from inclusion or exclusion criteria).
- **Intention-to-treat population (ITT):** This population consists of enrolled and randomized patients. All patients are evaluated in the arm to which they were assigned.
- **Per-protocol population (PP):** This population comprises patients who have fully adhered to the study protocol without major protocol deviations.

3.3. Flowchart

The following flowchart will be created :

4. Outcome measures

The analyses on overall survival will be conducted in the ITT population.

4.1. Primary outcome measure

The primary outcome is the 5-year overall survival. The time to overall survival is defined as follows:

- If the patient dies before the cut-off date*: Time between randomization and the patient's death, regardless of the cause.
- If the patient is alive at the cut-off date*: Time between randomization and the date of the last update**.

The maximum follow-up time is equal to the randomization date + 5 years, i.e., 60 months.

*The cut-off date is the date at which the data will be frozen. **The date of the last update can correspond to a visit date, a date of completion of the quality of life questionnaire, a start or end date of treatment, or an inter-cycle assessment date.

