6.6. Imputation

When a date is incomplete because only the day is missing, it will be imputed to the 15th of the month.

For the variable 'number of CRLM in quantitative form, regardless of the evaluation time, the following imputation will be performed: When the number in the category is strictly greater than 20, the number of nodules in quantitative form is uncountable. The number of nodules in quantitative form is then imputed as 25. This imputation will be done even in the case where a specific number of nodules is provided and that number is strictly greater than 25.

For the variables 'number of CRLM at inclusion', 'diameter of the largest CRLM at inclusion', 'Fong score at inclusion', the following imputation will be performed: The information is that provided at the last evaluation before randomization. When this data is not available, the information taken into account is that provided at the inclusion CT scan, and failing that, at the inclusion MRI.

For the ACE and CA19-9 markers at inclusion, the following imputation will be performed: The information is that provided at the last evaluation before randomization. When this data is not available, the information taken into account is that provided at inclusion.

For the ACE and CA19-9 markers at D0, the following imputation will be performed: The information is that provided at D0. When this data is not available, the information taken into account is that provided during the last assay in the month preceding transplantation.

Patients in arm C+LT who have undergone transplantation and have the chemotherapy type = NA are considered as not receiving adjuvant chemotherapy.

7. Interim analyses

No interim analysis is planned in this study

8. Sample size

The number of required events is 29. It aims to demonstrate a 40% difference in overall 5-year survival between the two randomization arms (50% for arm C+LT versus 10% for arm C) with a power of 90%, a two-sided alpha of 5%, and a follow-up loss rate of 2% and 10% in the C+LT and C arms, respectively. When we noticed that some patients in the C+LT arm did not receive LT, we re-estimated the number of events to 50 assuming that patients without LT would have a 10% survival rate and that patients with LT would have a 50% survival rate.

9. Statistical report

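### Section 4.1 counts deaths up to the data freeze but credits survivors only to their last update, so Kaplan-Meier survival at 3 and 5 years can be biased downward

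*SAP*

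**What the plan says.** Section 4.1 of the SAP defines the primary outcome with two rules.

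- Deaths: "If the patient dies before the cut-off date*: Time between randomization and the patient's death, regardless of the cause".
- Survivors: "If the patient is alive at the cut-off date*: Time between randomization and the date of the last update".

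The date that separates them is the freeze itself: "The cut-off date is the date at which the data will be frozen". Follow-up is capped: "The maximum follow-up time is equal to the randomization date + 5 years, i.e., 60 months". The footnote on updates reads "The date of the last update can correspond to a visit date, a date of completion of the quality of life questionnaire" and goes on to name treatment start or end dates and inter-cycle assessments. It names no vital-status contact.

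Section 3.1 lists as a protocol deviation: "Vital status or information on patient recurrence or progression is missing as of the last update". Neither that section nor 4.1 says how a patient with unknown status at the freeze enters the analysis. Section 4.2.1 carries the same definition to 3-year survival. Sections 4.2.2 and 4.2.3 use the same contrast of death against last update. Section 8 assumes "a follow-up loss rate of 2% and 10% in the C+LT and C arms, respectively".

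**The concern.** Kaplan-Meier, log-rank, Cox and RMST (section 6.3) all need censoring that does not depend on the outcome. Here, whether a patient stays at risk between the last update and the freeze depends on whether the patient dies in that interval. Take two patients last seen at month 57, both with a freeze after month 60. The one who dies at month 58 stays in the risk set and counts as an event. The one who is alive at the freeze is removed at month 57.

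The rule also sits badly with itself. To be classed as alive at the cut-off, a patient must be known to be alive then, yet the time is credited only to an earlier update.

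At stake is the 5-year survival percentage in each arm, which is the named primary outcome, and the 3-year percentage. The amount can differ by arm, because the hazards, the planned loss rates and the sources of update dates differ. Inter-cycle assessments follow chemotherapy, and one questionnaire is completed only in C+LT (section 4.2.5).

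**Working it through.** **Inputs from the SAP.** 5-year survival of "50% for arm C+LT versus 10% for arm C", loss of 2% and 10%, the 60-month cap and the two timing rules.

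**Inputs assumed, because the SAP does not give them.** Exponential survival; potential follow-up at the freeze, uniform over a stated range; the gap from last update to freeze, uniform from 0 to a stated maximum and unrelated to prognosis; contact lost at a uniform random time; every death before the freeze is learned.

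**Step 1: reproduce the plan's own figure.** HR = ln(0.50)/ln(0.10) = 0.301. With 1:1 allocation (assumed), the Schoenfeld formula gives 4 × (1.960 + 1.282)² / (ln 0.301)² = 29.16 events, against 29 in section 8. The survival model is therefore the plan's own. The events calculation is not affected by this point.

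**Step 2: the interval in question.** For a gap of g months, the chance of dying in it is 1 − S5^(g/60), where S5 is 5-year survival.

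- g = 3: C+LT 1 − 0.5^0.05 = 3.4%; C 1 − 0.1^0.05 = 10.9%.
- g = 6: C+LT 1 − 0.5^0.10 = 6.7%; C 1 − 0.1^0.10 = 20.6%.

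These patients count as deaths. The remaining patients contribute nothing over the same interval.

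**Step 3: effect on the estimate.** Simulation of 400,000 patients per arm under the rule as written, with 2% (C+LT) and 10% (C) lost. The true values are 50% and 10%. HR is the ratio of deaths per person-time, true value 0.301.

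| Follow-up at freeze (months) | Gap up to (months) | C+LT at 5 years | C at 5 years | HR |
|---|---|---|---|---|
| 60–96 | 3 | 50.0% | 9.8% | 0.300 |
| 60–96 | 6 | 49.6% | 9.7% | 0.302 |
| 36–96 | 3 | 49.4% | 9.3% | 0.301 |
| 36–96 | 6 | 48.8% | 9.0% | 0.303 |
| 24–84 | 3 | 49.1% | 8.9% | 0.300 |
| 24–84 | 6 | 47.9% | 8.5% | 0.305 |
| 12–72 | 6 | 46.5% | 7.6% | 0.305 |

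Runs with no gap and no loss gave 49.9% to 50.1% and 9.9% to 10.1%, so differences of 0.1 or 0.2 points are simulation noise. A further simulation under the same kind of assumptions puts the fall at about 0.2 to 0.3 points with at least 60 months of potential follow-up, and at about 1 to 2 points with 24 or 36 to 84 months. The RMST difference barely moved in those scenarios.

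**Step 4: less favourable cases, without lost contact.**

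- Gaps up to 12 months in both arms, follow-up 36–96 months: 47.9% and 8.8%, falls of 2.1 and 1.2 points, HR 0.307.
- Gaps up to 12 months in both arms, follow-up 12–72 months: 43.4% and 6.6%, falls of 6.6 and 3.4 points, HR 0.311.
- Gaps up to 12 months in C but 3 in C+LT: HR 0.298 with follow-up 36–96 months and 0.287 with 12–72 months.

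Equal gaps move the HR slightly toward 1. Longer gaps in C move it the other way.

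**Step 5: one clock for both.** Counting deaths and survivors alike only to the last update (36–96 months, gaps up to 6, 2%/10% lost) gives 50.1% and 10.0%, HR 0.300. The asymmetry, not the gap itself, causes the fall.

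**The case against.** Five arguments deserve weight.

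- **This is the usual convention: event at death, otherwise censor at last contact.** True in form. The difficulty arises when deaths are found beyond last contact and survivors are not followed to the same date. Section 4.1 does not prevent that, because it fixes both rules to the freeze.
- **The list of update dates is illustrative.** The footnote says what the update can be, so a vital-status contact is not excluded. Section 3.1 expects vital status to be recorded, and how it is checked may stand in the protocol. This stands: the SAP does not show that known survival time will be discarded, only that its named dates would allow it.
- **The cap limits the harm.** Deaths after month 60 do not count, and a survivor with an update at or after month 60 is credited in full. This also stands. It does not help patients whose last update falls earlier.
- **The comparison hardly moves.** A check with 45 patients per arm (an assumed size) and 3- or 6-monthly visits found the Cox HR shifted by at most 0.004 and log-rank power by at most 0.2 points. This stands for the test in section 6.3.
- **A freeze with only 12 months of minimum follow-up is unnatural for a 5-year endpoint with no interim analysis.** This is fair. Scenarios with falls near 7 points should not be read as the expected size.

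A reader might infer from the 2% and 10% loss that the arms will be biased unequally. Those are sample-size assumptions. They do not show that deaths are found among lost patients while survivors are not.

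**Conclusion.** The point holds as a weakness in the endpoint definition. The two rules in section 4.1 make censoring depend on outcome for patients last updated before month 60, and no other section removes this. The possible bias in Kaplan-Meier survival is downward.

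Under assumed contacts every 3 to 6 months and 2%/10% loss, it is a few tenths of a point with mature follow-up and about 1 to 2 points with 24 or 36 to 84 months. Larger falls need an early freeze or long gaps. The SAP fixes neither the freeze date relative to the last randomization nor a limit on the gap, so the size cannot be settled from it.

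It would be tempting to conclude that the primary result is biased, or that the treatment contrast is distorted. The documents support neither. The bias arises only if deaths are learned beyond last contact and updates are not current. In the scenarios tried the HR stayed between 0.287 and 0.311 against 0.301, with no consistent direction. The exposure is in the reported survival percentages. The change is worth making before the freeze, but it does not threaten the trial's test.

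**What to change.** Rewrite section 4.1 so that one clock applies to everyone:

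1. Set a single clinical cut-off date, before the freeze, for deaths and survivors alike.
2. Ascertain vital status for every ITT patient at that date, or at month 60 if earlier.
3. Count all deaths documented up to that date and within 60 months. Do not drop a death because it follows the last visit.
4. Censor patients confirmed alive at the cut-off at that date, at most 60 months.
5. Censor patients of unknown status at the date last known alive, and add a vital-status contact to the accepted update dates.
6. Report loss to follow-up by arm.
7. Add a sensitivity analysis that applies the last-update date to deaths and survivors alike. It covers what remains under item 5, where deaths among lost patients may still be learned more readily than survival.

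Section 4.2.1 then inherits the definition for 3-year survival. The cost is SAP wording and one vital-status check per surviving patient. No visits are added, and the number of events is unchanged.

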4.2. Secondary outcome measures

4.2.1. 3-Year overall survival

The 3-year overall survival is defined similarly to the primary outcome but at 3 years. The analysis will be conducted in the ITT population.

4.2.2. Comparison of progression-free survival at 3 and 5 years

In Arm C, progression is defined as the first progression occurring after randomization. In Arm C+LT, progression is defined as the first recurrence occurring after liver transplantation (LT).

The progression-free survival at 3 years is defined as follows:

- If the disease progresses one or more times before the cut-off date, and the first progression occurs within 3 years post-randomization: Time between randomization and the occurrence of the first progression.
- If the patient dies before the cut-off date without experiencing progression, and the death occurs within 3 years post-randomization: Time between randomization and death, regardless of the cause.
- If the patient is alive without progression at the cut-off date: Time between randomization and the date of the last update. The last update date will be a maximum of 3 years post-randomization.

The progression-free survival at 5 years is defined similarly but at 5 years. The analysis will be conducted in the PP population.

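### Progression-free survival counts different events in the two arms, in a per-protocol set that requires transplantation, so it favours C+LT even if transplantation does nothing

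*SAP*

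**What the plan says.** SAP Section 2.2 lists PFS at 3 and 5 years as a comparison between arms. Section 6.4 tests it by the method of the primary endpoint: log-rank and Cox, or restricted mean survival time (RMST) if hazards are not proportional.

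Section 4.2.2 runs the clock from randomization in both arms ("Time between randomization and the occurrence of the first progression") but defines the event by arm:

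- Arm C: "In Arm C, progression is defined as the first progression occurring after randomization".
- Arm C+LT: "In Arm C+LT, progression is defined as the first recurrence occurring after liver transplantation (LT".

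It then states: "The analysis will be conducted in the PP population". Section 3.2 keeps in PP only patients without a major deviation. Section 3.1 lists as major, for arm C+LT, "Patient not transplanted (major discrepancy" and also transplantation despite progression on the pre-LT scan. For arm C it lists "Patient who underwent LT or resection (major discrepancy" and not having received chemotherapy.

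Event-free patients are censored at the last update. Section 4.1 explains that the "date of the last update can correspond to a visit date, a date of completion of the quality of life questionnaire", or a treatment date.

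Section 8 records that some C+LT patients were not transplanted and that the required number of deaths was raised from 29 to 50 for that reason.

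**The concern.** Between randomization and LT, a retained C+LT patient cannot have a PFS event. Progression in that period is not an event by definition, and patients whose disease or death prevented LT are no longer in the data set. In arm C, every progression in the same period counts. This is guaranteed event-free time combined with selection on a post-randomization outcome, and both act in favour of C+LT.

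Nothing else in the SAP offsets it. The PP and ITT sensitivity analyses in Section 6.5 concern the primary endpoint only. No ITT, landmark or time-dependent analysis of PFS is stated. Recurrence-free survival and recurrence rate (Sections 4.2.3 and 4.2.4) are single-arm. PFS is therefore the trial's only between-arm comparison of progression, and as defined it is not a comparison of the groups as randomized.

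**Working it through.** **1. The same clinical course under the two sets of rules**

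| Course after randomization | Arm C (chemotherapy received) | Arm C+LT |
|---|---|---|
| Progresses early, never transplanted | Event at progression | Out of PP |
| Dies early, never transplanted | Event at death | Out of PP |
| Progression on pre-LT scan, then transplanted | Not applicable | Out of PP |
| Progresses earlier, is controlled, then transplanted | Not applicable | Stays in; that progression is not counted |
| First progression after the waiting period | Event | Event |

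The direction of the bias follows from this table and needs no assumption. Its size does.

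**2. How many C+LT patients were not transplanted**

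Section 8 gives no share, so it was inferred with the Schoenfeld formula, assuming 1:1 allocation: d = 4(1.960 + 1.282)² / (ln HR)² = 42.03 / (ln HR)².

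- Plan's first figure: HR = ln 0.5 / ln 0.1 = 0.301, so d = 42.03 / 1.441 = 29.2. This agrees with the stated 29.
- Revised figure: if a share q is not transplanted, 5-year survival in C+LT is 0.5(1 − q) + 0.1q. With q = 0.25 this is 0.40, HR = ln 0.4 / ln 0.1 = 0.398, and d = 42.03 / 0.849 = 49.5, rounded up to the stated 50. With q = 0.20 the result is 45; with q = 0.30 it is 56.

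About 25% is thus the share implied by the plan's own numbers.

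**3. Closed form with no LT effect**

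Assume the same exponential PFS in both arms with hazard λ = ln 2 / median, a fixed wait w, and loss before LT only through progression or death. Retained C+LT patients then have PFS of 1 up to w and S(t)/S(w) afterwards. If 25% are lost, S(w) = 0.75.

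- Every later PFS probability is multiplied by 1/0.75 = 1.33. With a median of 12 months, 3-year PFS is 0.5³ = 12.5% in arm C and 12.5% / 0.75 = 16.7% in C+LT.
- The median becomes w + true median, with w = median × ln(1/0.75) / ln 2 = 0.415 × median. That gives 6.0 vs 8.5, 9.0 vs 12.7 and 12.0 vs 17.0 months.
- The RMST fallback does not help. With a median of 6 months, λ = 0.1155 and w = 2.49. Over 36 months, arm C has (1 − e^(−36λ))/λ = 8.5 months and C+LT has w + (1 − e^(−λ(36 − w)))/λ = 11.0 months. The spurious gain is about 2.4 months.

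**4. Simulation with no LT effect**

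Exponential PFS with median 6 to 12 months.

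| Rule | Setting | HR (truth 1.00) | False positives |
|---|---|---|---|
| PP as written | Exponential wait, mean 2–4 months, 33 per arm | 0.75–0.90 | 7–19% two-sided (nominal 5%) |
| PP as written | Median 6, mean wait 3 months, 33 per arm | 0.79 | about 15–16% two-sided |
| PP as written | Wait set so that 25% are lost (mean 2.5–5.8 months), 45 per arm | 0.73–0.79 | 17–25% in favour of C+LT (nominal 2.5%) |
| Unequal event, ITT | As in the row above | 0.65–0.78 | 22–51% in favour of C+LT |
| Same event, ITT | As in the row above | 1.00 | 2–3% in favour of C+LT |

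In the second row the share lost before LT is λ/(λ + 1/3) = 0.1155/0.4488 = 26%, close to the implied 25%. The unequal-event ITT row also assumes that 10% of PFS events are deaths and that the death hazard after progression is 0.05 per month.

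**The case against.** - **PFS is secondary.** Overall survival at 5 and 3 years is analysed from randomization in ITT and is untouched. A spurious HR near 0.79 could not by itself produce a very large PFS effect. Both points stand. They limit the damage to this endpoint; they do not make its definition sound.
- **The two flaws overlap.** PP already removes most patients whose pre-LT progression would go uncounted, so the unequal event adds little within PP. The unequal-event ITT figures describe an analysis the SAP does not plan. This also stands. Those figures are here only to show that changing the population alone is not enough.
- **Arm C also loses patients from PP.** Those who never received chemotherapy are excluded, and some may be early failures. Assuming a mean of 0.5 to 1 month to the start of chemotherapy, the ratio of mean PFS in the 6-month/3-month scenario moves from about 0.80 to 0.84–0.88. The bias shrinks but remains.
- **The inputs are assumed.** The SAP does not say why patients missed LT. If some reasons were unrelated to prognosis, the selection part is smaller, but pre-LT events still cannot count. It is plausible, not documented, that arm C patients excluded for LT or resection were its better responders. Removing 10% of arm C from its better half would take HR 0.79 to 0.72, but that figure is illustrative only.
- **Censoring at the last update** is a separate, smaller matter, and its size was not estimated.

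**Conclusion.** The concern holds. As written, the PFS comparison is biased towards C+LT by its event definition and its population, and no other analysis in the SAP would reveal it. With no true LT effect, the expected HR is roughly 0.75 to 0.90 and the two-sided false-positive rate about 7% to 19% at 33 per arm. At the 25% non-transplant share implied by Section 8, the HR is 0.73 to 0.79.

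These sizes rest on assumed exponential PFS, waiting times, arm sizes and 1:1 allocation, and on pre-LT losses being due to progression or death. The direction does not. A modest PFS advantage for C+LT could not be attributed to LT. This must be corrected before the analysis, although the endpoint is secondary.

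**What to change.** Rewrite Section 4.2.2 as follows:

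1. **One event for both arms.** PFS is the time from randomization to the earlier of (a) first progression or recurrence at any time after randomization, before or after LT and whether or not LT was performed, or (b) death from any cause.
2. **ITT as the analysis population.** Any PP version should be labelled descriptive, with a statement that C+LT patients in it cannot have an event before LT. Items 1 and 2 are both needed.
3. **Censoring.** Censor event-free patients at their last tumour assessment, not at a questionnaire or treatment date.

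Outcome after transplantation remains described by the single-arm analyses in Sections 4.2.3 and 4.2.4.

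The cost is SAP wording, to be settled before the database is frozen, the point by which Section 10 requires the plan to be validated. Section 3.1 already treats missing progression status and dates as deviations without limiting this to transplanted patients, so the data appear to be intended for collection. Their completeness in non-transplanted C+LT patients should be confirmed. The PFS estimate for C+LT will be less favourable than under the present rule.

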4.2.3. Recurrence-free survival at 3 et 5 years in arm C+LT

The recurrence-free survival at 3 years is defined as follows:

- If the patient experiences one or more recurrences before the cut-off date, and the first recurrence occurs within 3 years post-randomization: Time between randomization and the occurrence of the first recurrence.
- If the patient dies before the cut-off date without experiencing recurrence, and the death occurs within 3 years post-randomization: Time between randomization and death, regardless of the cause.
- If the patient is alive without recurrence at the cut-off date: Time between randomization and the date of the last update. The last update date will be a maximum of 3 years post-randomization.

The recurrence-free survival at 5 years is defined similarly but at 5 years. The analysis will be conducted in patients randomized to Arm C+LT and who underwent LT.

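### PFS and recurrence-free survival are censored at a last-update date defined for overall survival, so time without a disease assessment can count as event-free

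*SAP*

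**What the plan says.** SAP section 4.2.2 gives the PFS rule for patients without an event: "If the patient is alive without progression at the cut-off date: Time between randomization and the date of the last update". Section 4.2.3 repeats it for RFS: "If the patient is alive without recurrence at the cut-off date: Time between randomization and the date of the last update". The only limit on the date is the time cap, for the 3-year endpoint "The last update date will be a maximum of 3 years post-randomization", with the 5-year endpoint defined in the same way.

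The term is defined once, in the footnote to the primary outcome in section 4.1: "The date of the last update can correspond to a visit date, a date of completion of the quality of life questionnaire", and further "a start or end date of treatment, or an inter-cycle assessment date". Sections 4.2.2 and 4.2.3 reuse the term without the footnote marks and offer no other definition.

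Two further places matter. Section 3.1 lists as a protocol deviation, for discussion at data review: "Vital status or information on patient recurrence or progression is missing as of the last update". It is not graded major or minor. On the population for PFS, section 4.2.2 says: "The analysis will be conducted in the PP population". RFS is instead analysed in patients randomised to C+LT who were transplanted.

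**The concern.** For overall survival, any contact proves that the patient is alive, so the last contact of any kind is a sound censoring date. PFS and RFS need more: the patient must be known to be free of progression or recurrence on that date. A returned questionnaire, or the start or end of a treatment, does not show this.

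Take a patient last scanned at month 30 who returns a questionnaire at month 36. Under the written rule the patient is progression-free to month 36, and six months without an assessment count as event-free follow-up. If this happens often, the PFS and RFS curves sit too high at the 3- and 5-year points that the SAP reports. The Kaplan-Meier recurrence rate (sections 4.2.4 and 6.4), which has no stated censoring date, would be too low if it takes the same rule.

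**Working it through.** **The plan's own figures.** The SAP states no figure for PFS or RFS censoring, so there is nothing to reproduce on this point. Its 29 events concern overall survival. They agree with the Schoenfeld formula at a hazard ratio of ln(0.5)/ln(0.1) = 0.301 (about 29.2 before rounding, 1:1 allocation assumed) and play no part here.

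**The text, side by side.**

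- Section 4.1: the last update may be a visit, a questionnaire, a treatment start or end, or an inter-cycle assessment.
- Sections 4.2.2 and 4.2.3: event-free patients are censored at the last update, subject only to the cap.
- Nowhere is the date tied to imaging or documented disease status for these endpoints.
- Section 3.1 treats missing progression information at the last update as a deviation. The SAP thus foresees that the two can separate, but gives no censoring rule for that case.

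**Direction.** At a time with d observed events, let n patients still be under disease assessment and m be followed by contact only. The Kaplan-Meier factor is 1 − d/(n + m) under the present rule and 1 − d/n under censoring at the last assessment. Whenever d and m are above zero, the first is larger. This presumes that progression among the m patients goes unrecorded.

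**Size, under assumptions.** None of the following inputs is in the SAP: exponential time to progression with a median of 6, 12, 18 or 24 months; scans every 3 months, with progression detected at the next scan; 10% or 30% of patients stopping scans at a random time in the first 36 months; non-imaging contact 3, 6 or 12 months after the last scan; no deaths without progression. With 40,000 simulated patients per scenario, event-free probability at 36 months (last contact v last scan, %) was:

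| Median (months) | Stopping scans | Gap 3 months | Gap 6 months | Gap 12 months |
|---|---|---|---|---|
| 6 | 10% | 1.6 v 1.6 | 1.6 v 1.4 | 1.9 v 1.5 |
| 6 | 30% | 1.8 v 1.6 | 2.1 v 1.5 | 3.4 v 1.6 |
| 12 | 10% | 12.7 v 12.5 | 13.1 v 12.6 | 13.8 v 12.7 |
| 12 | 30% | 13.3 v 12.4 | 14.1 v 12.4 | 16.4 v 12.6 |
| 18 | 10% | 25.4 v 25.1 | 25.2 v 24.6 | 26.4 v 25.1 |
| 18 | 30% | 26.3 v 25.2 | 27.7 v 25.4 | 29.4 v 24.9 |
| 24 | 10% | 35.6 v 35.3 | 36.1 v 35.4 | 36.9 v 35.6 |
| 24 | 30% | 36.9 v 35.8 | 37.9 v 35.6 | 39.9 v 35.5 |

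The overstatement is at most 1.8 points in 19 of the 24 scenarios. The other five all have 30% stopping scans and a gap of 6 or 12 months; they run from 27.7 − 25.4 = 2.3 to 29.4 − 24.9 = 4.5 points. Censoring at the last scan agreed with complete scanning to within about 0.1 point throughout.

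A second simulation used 47 patients per arm (assumed), medians of 9 to 12 months in C and 20 in C+LT, loss to follow-up of 10–20% v 2%, and imaging ending at most 3 to 6 months before last contact. Three-year PFS rose by 0.2 to 0.9 points in C and 0.4 to 1.2 in C+LT. Five-year PFS in C+LT rose by 0.7 to 1.7 points, for example from 12.8% to 14.5% (1.7/12.8, about 13% relative). The bias vanished when scan and contact dates coincided.

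**Between-arm comparison.** In a check over similar scenarios (600 replicates), the PFS hazard ratio moved by at most about 0.008, for example from 0.573 to 0.581. The 3-year difference between arms moved by about 0.5 point or less, against a sampling standard deviation of about 8 points.

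**The case against.** Several points on the other side have force.

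- **The rule permits the problem but does not impose it.** The last update may be a visit or an inter-cycle assessment, and either may include disease evaluation. A reader might infer that unassessed time is counted for every event-free patient. The SAP does not support that; it depends on the imaging and contact schedule, which is not in the document. This objection stands.
- **Bias that differs by arm.** A reader might also infer that the arms are affected unequally and that the PFS comparison is distorted. The SAP has a third questionnaire in C+LT only (section 4.2.5) and assumes different losses to follow-up, 2% v 10% (section 8). But the other two questionnaires are used in both arms, and section 6.6 refers to adjuvant chemotherapy in transplanted patients, so treatment dates can arise there too. Nothing shows that scan-to-contact gaps differ by arm, and the simulated shift in the comparison is very small. This objection stands too.
- **The deviation item in section 3.1 is a safeguard.** It could flag the month-30/month-36 patient and, if graded major, remove that patient from the per-protocol population used for PFS. This stands only in part: the item is ungraded, leaves the censoring date unchanged, and cannot protect RFS, which is not analysed in that population.
- **The remedy has a bias of its own.** Deaths from any cause are events. Censoring survivors at the last assessment while counting deaths learnt of later can pull the estimates down slightly. The grid above contains no deaths without progression, so it does not show the remedy to be unbiased for these composite endpoints. This is a fair caveat, and keeping the present rule as a sensitivity analysis answers it.

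**Conclusion.** The concern holds as a fault in a rule that the SAP states, not as a gap left to the protocol. For PFS and RFS the censoring date is borrowed from overall survival and may carry no information on disease status, so the Kaplan-Meier estimates can be too high.

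The size rests wholly on assumptions, because the SAP gives no scan schedule or contact pattern. Plausible scenarios give about 0 to 2 points; about 4.5 points at 36 months needs 30% of patients to stop scans and a 12-month gap. An effect on the between-arm PFS comparison is possible but not shown. Only secondary endpoints are involved, RFS is descriptive (section 6.4), and the primary analysis is untouched. The change is worth making before the database is frozen, because it is cheap and should be settled before results are seen.

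**What to change.** In sections 4.2.2 and 4.2.3, censor patients without an event at the date of the last assessment documenting absence of progression or recurrence, capped at 36 or 60 months after randomisation. State the same rule for the Kaplan-Meier recurrence rate in sections 4.2.4 and 6.4. Keep the last-update date for overall survival, and keep the present rule as a sensitivity analysis for PFS and RFS.

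The cost is a few sentences in the SAP and the use of disease-assessment dates in programming. Censored follow-up becomes slightly shorter and the PFS and RFS figures slightly less favourable. A small downward bias is possible because deaths found after the last assessment still count as events; the sensitivity analysis shows how much the choice of rule matters.
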